10. SAFETY ANALYSES

All safety tables, listings and figures will use the Safety population unless specified otherwise.

10.1. Adverse Events

A listing of all new problems during the hospital stay, including nosocomial infections, will be produced.

In addition, any ongoing illnesses, as collected on the daily monitoring chart, will be listed.

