4. ANALYSIS POPULATIONS

The following populations will be defined:

Safety population: The safety population will comprise all randomised subjects who start the SAM Routine Standard of care (with or without topical application of SSO) and will be used for the analysis of safety data. The data will be analysed according to the actual treatment received if this differs from the treatment to which the subject was randomised. If subjects receive treatment differing from that assigned by the randomisation schedule (for either a portion of or the entire time on study), they will be

analysed based on the treatment taken for the majority (>50%) of their time on study treatment.

Intent-to-Treat (ITT) population: This will consist of all randomised subjects from whom at least baseline and at least one post baseline measure have been obtained and will be used for the analysis of efficacy data. The data will be analysed according to the treatment to which the subject was randomised.

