9.2. Time (days) to discharge from acute phase

Derivations

Discharge from the acute phase is based on improvement in mental state, normalisation of vital signs, re-establishment of oral feeding and resolution of all acute illnesses.

The CRF collects information on whether a patient is ready for discharge from the acute phase (Y/N) daily. Time (days) will be derived as the number of days between baseline and the first occurrence where 'Ready for discharge from acute phase' was recorded as Yes. Baseline will be taken as the earliest measurement recorded in the daily monitoring chart. Day will be derived relative to the baseline.

If a subject withdrew or died before being ready for discharge from the acute phase then they will be censored at the time they left the study. Patients who completed Day 10 before being ready for discharge will be followed up by the site until they withdraw or are ready for discharge.

Kaplan Meier

A Kaplan-Meier plot including 95% CIs and the number of subjects at risk at each day will be presented.

Cox Proportional Hazards

The time to discharge from acute phase will be compared between treatment groups using a Cox's Proportional Hazards model adjusting for the covariates specified in Section 7.1.

The time to discharge from acute phase will be presented in quartiles for each group. The hazard ratio, 95% CI and associated p-value will also be presented.

Residual plots from the Cox proportional hazard model and the Kaplan-Meier plot will be used to visually check the assumption of proportional hazards is fair. If the proportional hazard assumption is invalid, then other methods of analysis may be considered which do not make this assumption, for example a Weibull model may be fitted to the data.

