10.2. Concomitant Medications

A listing of all antibiotics given during the study will be produced. Antibiotics that were taken prior to the start of the study will not be included.

The listing will also include the duration of the concomitant medication prescription. This will be reported as the total number of days prescribed. Following the interim analysis discussions, a separate listing will be provided restricting the duration to the number of days that the concomitant medication taken during the study. For example, if a child on day 8 was prescribed 14-days' worth of concomitant medication then the first listing would record this as '14' and the second would record this as '3' i.e. the concomitant medication was taken on study day 8, 9 and 10.

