10.3. Laboratory Measurements

A listing of the complete blood count and other biochemical / serological investigations laboratory data collected during the study will be produced.

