10.4. Vitals Signs

Pulse, temperature, respiratory rate and mental status (Normal / irritable / lethargic) were collected three times a day. This data will be listed.

Supplemental Table 1. Emollient (sunflower seed oil) composition

Product description:

Refined sunflower oil is a vegetable oil of non-GM origin and is non-hydrogenated.

Compliance with Food legislation:

This product complies with all current and relevant requirements, which are set by EU food legislation. Cargill's "Standards on Unwanted Components" is available upon request and contains legal limits for contaminants, quality and food safety parameters.

TECHNICAL SPECIFICATIONS ¹⁾ Min Max Reference method²⁾ Sensory: bland Cargill Internal method Taste -Appearance at room temperature clear Cargill Internal method _ Chemical: Free Fatty Acid, as oleic 0.10 EN-ISO 660:2009 % Peroxide Value, at bottling meq/kg 2.0 ISO 3960:2007 _ Moisture Content 0.10 ISO 8534:2007 % -Colour Lovibond 5.25" ISO 15305:1998 Red 2.0 -**Fatty Acid Composition:** EN-ISO 5509:2000 & EN-ISO 5508:1995 C16:0 % 5.0 7.6 2.7 C18:0 % 6.5 C18:1 (total) % 14.0 39.4 C18:2 (total) 48.3 74.0 % % 0.5 C18:3 (total) -Trans fatty acids (total) % 2.0

1) Analyses are done by our refineries/ suppliers before reception of the oils in the bottling plant

2) Cargill reserves the right to use internal analytical method that is in compliance with the International Reference Method

Supplemental Table 2: Skin condition score assessment

Score	Skin Description		Day O		Day 2		Day 4		Day 6		Day 8		Day 10
		Area (%)	Locations										
0	Normal, no sign of dry skin or scaling												
1	Skin dry, no visible scales												
2	Skin dry with fine scales												
3	Skin dry with scales and fissures, no erythema												
4	Dry skin with scales, fissures and erythema												
5	Dry skin with scales, fissures, erythema and focal areas of crusting and/or oozing												
6	Dry skin with scales, fissures, 10% body surface area with erythema, crusting and/or oozing												
7	Nearly entire skin is erythematous and/or oozing												
8	Vesicles or pustules present												
	Total Score												

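### Section 10 only lists new problems and antibiotics: apart from four infections, withdrawals and skin or inflammatory outputs, harms get no by-arm summary, and the new-problems listing has no stated cut-off

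*SAP*

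**What the plan says.** Section 4 defines a Safety population for the safety analysis and groups it by treatment actually taken: "The data will be analysed according to the actual treatment received if this differs from the treatment to which the subject was randomised". The opening line of section 10 assigns that population to safety tables, figures and listings alike.

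The four subsections then specify only listings:

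- 10.1, new problems: "A listing of all new problems during the hospital stay, including nosocomial infections, will be produced".
- 10.1, ongoing illnesses: "In addition, any ongoing illnesses, as collected on the daily monitoring chart, will be listed".
- 10.2, antibiotics: "A listing of all antibiotics given during the study will be produced". After the interim discussions a second version was added: "a separate listing will be provided restricting the duration to the number of days that the concomitant medication taken during the study".
- 10.3, laboratory data: "A listing of the complete blood count and other biochemical / serological investigations laboratory data collected during the study will be produced".
- 10.4, pulse, temperature, respiratory rate and mental status: "This data will be listed".

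No count, percentage, rate or interval by arm is specified in any of them.

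**The concern.** The stated objective is the benefit of a repeatedly applied topical oil in severely malnourished children from 2 months of age. To weigh that benefit, a reader needs at least the number and percentage of children in each arm with a new problem, by type. A listing contains the events but does not total them, so a reader would have to count by hand, choosing the window and the denominator alone. The plan sets up an as-treated population with a majority rule for mixed treatment, and then gives it no adverse-event table to serve.

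**Working it through.** No arithmetic applies: the SAP gives no event rate, arm size or safety margin, and no figure to reproduce. The check sets the outputs side by side.

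**1. Section 10.** By-arm summaries specified: none in 10.1, 10.2, 10.3 or 10.4. That is four listing-only subsections out of four.

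**2. Harm-type outcomes summarised by arm elsewhere.**

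| Section | Outcome | Output | What it leaves open |
|---|---|---|---|
| 8.1 | Premature withdrawal | n and % with reasons, Safety population | Death is not named as a reason category |
| 9.3 | Suspected pneumonia, fever, UTI, sepsis | n and % by arm, type and age category; logistic regression | Four types only, identified at the interim results meeting; ITT population; regression may be dropped if infections are few, with no threshold |
| 9.4, 9.5 | TEWL, skin redness | By-arm summaries and repeated-measures model | Measurements, not events |
| 9.6 | Skin appearance | Total score summarised and modelled | Components, including vesicles or pustules, are not summarised |
| 9.7 | SCORDoK manifestations | n and % by day and arm, some graded; also by age category | Presence on Days 0, 2, 4, 6, 8 and 10, not new onsets |
| 9.9, 9.10 | CRP, cytokines | By-arm summaries at Day 0 and Day 10 | Markers, not events |

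**3. What remains without a by-arm summary.**

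- New problems other than the four infections. Skin infection is one: 8.3 tabulates it by arm at Day 0, but after baseline it is only listed.
- Deaths as a named row. Section 9.2 recognises death as a way of leaving the study, but no table is said to show it.
- Antibiotic use. Section 10.2 already derives the on-study duration for each child (its example reduces a 14-day prescription on day 8 to days 8, 9 and 10, that is 3 days), yet nothing totals it by arm.

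**4. Population.** The one comparison of adverse events, in 9.3, uses the ITT population, because section 9 applies that population to all efficacy outputs. By section 4, ITT needs a baseline and at least one post-baseline measure, and follows randomisation. The Safety population needs only randomisation and start of standard care, and follows treatment received. It supports disposition, demography and baseline tables (8.1 to 8.3), but no adverse-event comparison.

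**5. Window.** Section 9.3 counts infections whose symptoms began in the 10-day treatment period. The second listing in 10.2 stops at Day 10. The new-problems listing in 10.1 refers to the hospital stay and states no end day.

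**The case against.** The strongest reply is that the plan compares a good deal of harm already. Local skin worsening, the most plausible harm of an oil on the skin, is covered by four sections, 9.4 to 9.7. Infections are compared over a fixed period, and withdrawals are tabulated in the Safety population. The study is exploratory and open-label, with benefit as its stated objective, so formal safety testing is not called for.

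Much of this stands. A reader might infer from section 10 that the trial gives no comparison of harm at all. The outputs in 8.1, 9.3 to 9.7, 9.9 and 9.10 contradict that, and calling most of them efficacy outputs does not change what they compare. The exploratory label excuses the absence of tests and multiplicity control. It does not explain why a simple count by arm is missing for the remaining events.

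A reader might also infer that events are counted over stays of unequal length, which would favour the arm that leaves sooner. Section 9.2 invites this: "Patients who completed Day 10 before being ready for discharge will be followed up by the site". The documents do not carry it that far. That sentence concerns readiness for discharge from the acute phase, which is not shown to be the same as leaving hospital. Nothing says that new problems are recorded after Day 10, and by section 7.2 the daily monitoring chart ends at study Day 10. Nor does the hospital-stay wording extend to antibiotics or laboratory data, which 10.2 and 10.3 list over the study. A bias of a given size would rest on assumed stays, so none is claimed.

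**Conclusion.** The point holds in a limited form. Followed as written, the SAP gives no by-arm summary of new problems outside four infections, of deaths as a named category, or of antibiotic use, and it makes no adverse-event comparison in the as-treated Safety population. The new-problems listing lacks the explicit cut-off that 9.3 and the second antibiotic listing have. This is a gap in stated outputs and not an error in any figure. It does not affect the weight-gain analysis. How many events it concerns cannot be known from the SAP.

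The conclusion assumes that no further safety table is specified outside this document, and that the recorded new problems carry a type and a start date so that they can be tabulated. The SAP already relies on symptom onset for the infections in 9.3.

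**What to change.** **10.1:** add one descriptive table in the Safety population, by treatment received and also split by the two age strata, for onsets from Day 0 to Day 10 as labelled in 7.2. Rows: children (number and %) with any new problem; with each type, showing skin infection and new skin reactions separately; and deaths. Give a risk difference with 95% CI for any new problem overall only. State the Day 10 cut-off, and list any later onsets separately.

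**10.2:** add a by-arm summary of the number and % of children given any antibiotic, and of on-study antibiotic days per child, using the within-study duration already derived there.

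**Cost:** SAP wording and two extra tables from data already collected. Rows by type and age stratum may hold few events. With an open-label design and no multiplicity adjustment (6.2), they should be read descriptively.

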10.2. Concomitant Medications

A listing of all antibiotics given during the study will be produced. Antibiotics that were taken prior to the start of the study will not be included.

The listing will also include the duration of the concomitant medication prescription. This will be reported as the total number of days prescribed. Following the interim analysis discussions, a separate listing will be provided restricting the duration to the number of days that the concomitant medication taken during the study. For example, if a child on day 8 was prescribed 14-days' worth of concomitant medication then the first listing would record this as '14' and the second would record this as '3' i.e. the concomitant medication was taken on study day 8, 9 and 10.

10.3. Laboratory Measurements

A listing of the complete blood count and other biochemical / serological investigations laboratory data collected during the study will be produced.

10.4. Vitals Signs

Pulse, temperature, respiratory rate and mental status (Normal / irritable / lethargic) were collected three times a day. This data will be listed.

Supplemental Table 1. Emollient (sunflower seed oil) composition

Product description:

Refined sunflower oil is a vegetable oil of non-GM origin and is non-hydrogenated.

Compliance with Food legislation:

This product complies with all current and relevant requirements, which are set by EU food legislation. Cargill's "Standards on Unwanted Components" is available upon request and contains legal limits for contaminants, quality and food safety parameters.

TECHNICAL SPECIFICATIONS ¹⁾ Min Max Reference method²⁾ Sensory: bland Cargill Internal method Taste -Appearance at room temperature clear Cargill Internal method _ Chemical: Free Fatty Acid, as oleic 0.10 EN-ISO 660:2009 % Peroxide Value, at bottling meq/kg 2.0 ISO 3960:2007 _ Moisture Content 0.10 ISO 8534:2007 % -Colour Lovibond 5.25" ISO 15305:1998 Red 2.0 -**Fatty Acid Composition:** EN-ISO 5509:2000 & EN-ISO 5508:1995 C16:0 % 5.0 7.6 2.7 C18:0 % 6.5 C18:1 (total) % 14.0 39.4 C18:2 (total) 48.3 74.0 % % 0.5 C18:3 (total) -Trans fatty acids (total) % 2.0

1) Analyses are done by our refineries/ suppliers before reception of the oils in the bottling plant

2) Cargill reserves the right to use internal analytical method that is in compliance with the International Reference Method

Supplemental Table 2: Skin condition score assessment

Score	Skin Description		Day O		Day 2		Day 4		Day 6		Day 8		Day 10
		Area (%)	Locations										
0	Normal, no sign of dry skin or scaling												
1	Skin dry, no visible scales												
2	Skin dry with fine scales												
3	Skin dry with scales and fissures, no erythema												
4	Dry skin with scales, fissures and erythema												
5	Dry skin with scales, fissures, erythema and focal areas of crusting and/or oozing												
6	Dry skin with scales, fissures, 10% body surface area with erythema, crusting and/or oozing												
7	Nearly entire skin is erythematous and/or oozing												
8	Vesicles or pustules present												
	Total Score												

Score of all calculation method: For skin scoring we multiplied the area (%) of involvement with the corresponding category's score. The each % of area correspond the score of that category. For example: in line number three, 'Skin dry with fine scales' corresponds the socre '2', so each % of skin area with such characteristic will get 'X' % x 2 score. Total skin appearance score will be the summation available score in individual column.

Location code and % of area:

Location	Code	Area (%)	Location	Code	Area (%)
Head, anterior	HA	9	Upper trunk, anterior	UTA	9
Head, Posterior	HP	9	Upper trunk, Posterior	UTP	6.5
Rt. Upper arm, Anterior	Rt.UAA	2.25	Lower trunk, anterior	LTA	9
Rt. Upper arm, Posterior	Rt.UAP	2.25	Lower trunk, posterior	LTP	6.5
Rt. Lower arm, Anterior	Rt.LAA	2.25	Lt. Buttock	Lt.BT	2.5
Rt. Lower arm, Posterior	Rt. LAP	2.25	Rt. Buttock	Rt.BT	2.5
Lt. Upper arm, Anterior	Lt.UAA	2.25	Rt. lower leg, anterior	Rt.LLA	3.5
Lt. Upper arm, posterior	Lt.UAP	2.25	Rt. lower leg, posterior	Rt.LLP	3.5
Lt. Lower arm, Anterior	Lt. LAA	2.25	Lt. upper leg, anterior	Lt.ULA	3.5
Lt. Lower arm, Posterior	Lt. LAP	2.25	Lt. upper leg, posterior	Lt.ULP	3.5
Rt. Upper leg, anterior	Rt.ULA	3.5	Lt. lower leg, anterior	Lt.LLA	3.5
Rt. Upper leg, posterior	Rt.ULP	3.5	Lt. lower leg, posterior	Lt.LLP	3.5
		Total = 100 %
